- **Table 2:** Schedule of activities for the iBeChange Pilot Study. 13**Table 3:** Objectives and endpoints in the iBeChange Pilot Study
- Table 4: Inclusion and Exclusion criteria for the iBeChange Pilot Study
- Table 5: Inclusion and Exclusion criteria for the iBeChange Wearable Sub-Study
- **Table 6:** Recruitment centres: characteristics and expected recruitment size for the iBeChange Pilot Study.
- **Table 7:** Criteria for intervention escalation to Level 1, Level 2 and Level 3 in the iBeChange platform for each health pillar.
- **Table 8:** Estimated recruitment per cancer screening type and clinical centre for the wearable sub-study

List of Figures

- Figure 1: iBeChange Pilot Study Flow Diagram.
- Figure 2: Participant's health habit status visualisation in the iBeChange platform
- Figure 3: Participant's journey in the iBeChange platform
- **Figure 4:** Logistics workflow for wearable assignment depending on recruitment status and size availability.
- Figure 5: Data Flow Diagram: Data processing for the iBeChange pilot study.
- Figure 6: Participant recruitment and data flow diagram.

Executive Summary

The **iBeChange pilot study protocol** outlines the design and implementation of a 12-week digital health intervention aimed at promoting behavioural change for cancer prevention across five lifestyle and psychosocial health pillars: smoking, alcohol consumption, nutrition, physical activity, and emotional well-being. The pilot study will evaluate the feasibility, usability, and preliminary effectiveness and cost-effectiveness of the iBeChange platform prior to the launch of a randomised controlled trial (RCT).

This protocol includes the **wearable sub-study**, which forms part of the same **randomisation strategy** as the main pilot study. Participants in the intervention group will be further randomised to either receive or not receive a wearable device (Oura ring), enabling passive lifestyle data collection. This integrated design ensures consistency in participant allocation and adherence to methodological standards required for ethical approval. The Ethical approval for this pilot study protocol is expected to be obtained shortly. Deliverable 5.1 will be updated once approved by the Institutional Review Boards.

While the wearable sub-study is incorporated into this protocol submission to facilitate joint ethical committee approval, a dedicated deliverable (D5.2: iBC/WS protocol approval and registration) has been prepared, providing specific information regarding the wearable component, including procedures, data handling, and specific research objectives.

The outcomes of this pilot will inform the optimisation of the platform, recruitment strategy, and intervention delivery ahead of the full-scale RCT, ensuring scientific rigor and participant engagement are maintained.

1. Introduction

This deliverable presents the pilot study protocol for the iBeChange (iBC) project, developed under Work Package 5 (WP5) – Deployment of the Recommendation System to the Population. WP5 aims to design and implement prospective studies to evaluate the feasibility, usability, and preliminary impact of the iBeChange platform—a digital health solution promoting behavioural change for cancer prevention.

The pilot study (iBC/PS) represents the initial and critical phase of WP5. It is designed to test and refine all essential components related to participant recruitment, study management, intervention delivery, and data collection procedures across participating clinical sites. The findings of this pilot will directly inform the subsequent multicentre randomised controlled trial (iBC/CT), which will assess the long-term effectiveness, cost-effectiveness and implementation of the iBC platform.

This protocol was developed collaboratively by clinical, technical, statistical and data management partners in accordance with Task 5.1 – Pilot Preparation and supports the activities of Task 5.4 – Pilot Study and Data Management. It will also contribute to Task 5.2 – Study Management and Supervision, which includes oversight by the Trial Supervision Committee.

This protocol also includes the wearable sub-study, a nested component of the pilot trial. The wearable sub-study has been included as it is part of the same randomisation strategy as the main pilot. It aims to assess the feasibility of using digital devices (i.e., Oura Ring) to collect behavioural and psychosocial data passively. While included here for ethical submission purposes, additional details and procedures specific to the wearable component are described in a separate deliverable (D5.2 – iBC/WS Protocol Approval and Registration).

This document provides a detailed overview of the pilot's objectives, design, methodology, and ethical considerations, aligning with WP5's overarching goal of preparing for the scaled deployment and validation of the iBeChange recommendation system.

2. Protocol Summary

2.1. Synopsis

Table 1. iBeChange Pilot Study Synopsis

[figure not shown]
Title:	Behavioural change for cancer prevention: A pilot study protocol of a digital intervention		
Grant Number:	Horizon Mission Cancer HORIZON-MISS-2023-CANCER-01 ID: 101136840		
Study Description:	This pilot study will assess the feasibility of iBeChange, a digital platform designed to promote personalised behavioural change to address lifestyle and psychosocial risk factors associated with cancer risk. Twelve weeks of iBeChange intervention will be compared to treatment as usual, consisting of receiving general cancer prevention guidelines. A sub-group of participants in the iBeChange intervention group will receive an Oura ring wearable device to automatically and unobtrusively collect physiological data.		
Objectives*:	The primary objective of this pilot study is to assess the feasibility of iBeChange in real-life settings.		
	Additionally, preliminary data regarding the effectiveness and cost-effectiveness of iBeChange compared to general cancer prevention guidelines will be collected.		
	Also, exploratory data from Oura smart rings will be collected from the allocated participants.		
	Finally, usability and satisfaction will be assessed for the iBeChange platform and for the selected wearable devices.		
Endpoints*:	The primary endpoints are the feasibility of the recruitment, data collection, and ability to manage and implement the study and intervention.		
	The secondary endpoints are the effectiveness and cost-effectiveness of iBeChange in achieving a sustainable behavioural change in Smoking, Alcohol consumption, Nutrition, Physical activity habits, and Emotional Wellbeing symptoms.		
Study Population:	This pilot study will enrol a total of 180 healthy individuals (60 per clinical centre), both men and women, aged 45-80 who undergo screening tests for breast, colorectal or lung cancer, from Spain, Italy and Romania.		
Phase * or Stage:	Not Applicable (Behavioural Intervention)		
Description of Sites/Facilities Enrolling Participants:	This pilot study is a European multicentric trial. It will be conducted in the centres: Institut Català d'Oncologia (ICO, Barcelona, Spain), Istituto Euro di Oncologia (IEO, Milano, Italy), and Universitatea de Medicina si Farm Carol Davila (UMFCD, Bucarest, Romania).		

Description of Study Intervention/Experimental Manipulation:	The study intervention consists of a digital platform promoting behavioural change towards healthier habits focused on primary cancer prevention. Individuals from the experimental group will have access to the iBeChange platform for 12 weeks, used as a smartphone application.		
Study Duration *:	8 months		
Participant Duration:	12 weeks		

2.2. Schema

The following schema (Figure 1) indicates the activities to be accomplished at each time point for the iBeChange pilot study.

Figure 1. iBeChange Pilot Study Flow Diagram

2.3. Schedule of activities

The schedule on the next page indicates the procedures that will be accomplished at each study time (Table 2).

Table 2. Schedule of activities for the iBeChange Pilot Study (next page)

	Pre- screening (Pre- consent)	Screening Day 0 In-person	Time 1 Baseline Day 0	Time 2 Post- intervention Day 90 ± 7
Phone call to review for eligibility and invitation to the study	X			
Informed Consent		Х		
Demographics and contact information		Х		
Randomisation		Х		
Outcome Evaluation				
Primary - Feasibility outcomes:				
 Recruitment Capability and Resulting Sample Characteristics 				
 Data Collection and Outcome Measures Answer Rate 	X	X	X	X
 Acceptability and Suitability of Intervention and Study Procedures 				
 Resources and Ability to Manage and Implement the Study and Intervention 				
Secondary - Behavioural change and Psychosocial outcomes:				
 Seven-day point prevalence abstinence 				
Change in Smoking habits			X	х
 Fagerström test for Nicotine Dependence (FTND) 				
 Alcohol Use Disorders Identification Test (AUDIT) 				
Secondary - Behavioural change and Psychosocial outcomes (cont.):				
iBeChange-Diet questionnaire on Cancer Nutritional factors			х	X
Height and Weight for BMI calculation				

	Pre- screening (Pre- consent)	Screening Day 0 In-person	Time 1 Baseline Day 0	Time 2 Post- intervention Day 90 ± 7
Global Physical Activity Questionnaire (GPAQ)				
 Perceived Stress Scale (PSS-4) 				
 Patient Health Questionnaire (PHQ-4) 				
 Perceived Social Support (F-SozU K- 3) 				
Secondary - Cost-effectiveness outcomes			Х	Х
Tertiary				
Voice analysis Informed Consent (optional)		Х		
Wearable sub-study Informed Consent		Х		
Wearable device delivery		Х		
Wearable device return				Х

3. Background

3.1. Study Rationale

Every year, 20 million citizens are diagnosed with cancer worldwide, a number that keeps increasing constantly. Lung, colorectal and breast cancer are the three leading oncological diagnoses in terms of mortality, accounting for more than 40% of deaths, but also in terms of incidence, together with prostate cancer.²

Research has shown that certain risk factors increase a person's chances of developing a variety of cancers.³ Such risk factors include those that cannot be controlled (e.g., age or family history), as well as those that could be modified, such as health behaviours and exposures to known environmental carcinogens.⁴

A recent study by Islami et al. (2018) estimated that 42% of all cancers diagnosed and 45% of all cancer deaths in the last years were attributable to modifiable behavioural factors, including tobacco use, alcohol consumption, unhealthy nutrition and obesity, and lack of physical activity. Specifically, 90% of lung cancer cases, 55% of colorectal cancer cases, and 25% of breast cancer cases in Europe are related to modifiable factors, suggesting these diagnoses are, to some extent, preventable. 4

The recent growing literature on modifiable cancer risk factors focuses on the interaction between health behaviours and psychosocial factors (e.g., depression, anxiety, recent loss events, social support, general distress), which could also be addressed.⁶

The process of intentionally altering a behaviour is known as behavioural change (BC). Behaviour change often has two primary objectives: starting or increasing healthy behaviours, such as exercising, or stopping or reducing unhealthy behaviours, like smoking. BC can involve setting goals, developing a plan of action, and tracking progress over time. Certain unhealthy behaviours such as smoking, drinking alcohol or eating junk food are often intertwined with emotional management (EM). EM is the ability to regulate one's emotions in response to different situations. Although BC and EM are distinct concepts, they strongly influence one another. For example, individuals experiencing anxiety may find it more challenging to quit drinking, as alcohol can provide short-term relief while ultimately increasing the risk of anxiety disorders. Therefore, strengthening EM skills—such as coping strategies for anxiety—can significantly improve the likelihood of successfully adopting and maintaining healthier habits. Given the large number of cancer incidence and deaths worldwide caused by potentially modifiable behavioural, environmental, and psychosocial factors, widespread programs promoting BC and EM are necessary to reduce cancer incidence.

To improve the generally low accessibility of health care programs, delivering services depending on the person's needs could result in a sensible and compromised solution. Stepped-care interventions, designed to adjust to people's changing demands, enable to overcome the challenge of offering support with fewer health resources.^{8,9} To do so, more and more digital platforms such as smartphone or web-based applications have been conceived to improve assessment and stepped intervention delivery.¹⁰

Digital health BC interventions are increasingly popular and widely accessible tools to foster and support BC for the maintenance and improvement of health. Likewise, digital health (eHealth) interventions offer a promising and accessible option to promote mental health. Specifically, eHealth interventions for improving EM of healthy individuals through mindfulness and social support have shown effectiveness among psychologically distressed populations. ¹²

Over the past few years, the field of mobile health (mHealth) has seen a rapid increase in the use of artificial intelligence (AI) to promote healthy behaviour change. ¹³ In particular, the integration of AI into mHealth interventions has shown great promise in facilitating the adoption of healthy lifestyle behaviours, such as regular physical activity, healthy eating habits, and tobacco or alcohol cessation. AI algorithms can be used to analyse data from an individual's behaviour, such as their activity levels and lifestyle habits, to develop personalised treatment plans that target their specific needs. Studies have demonstrated that mHealth interventions can be effective in promoting healthy behaviours by providing personalised feedback, reminders, and recommendations based on individual data. The AI component of the intervention has shown capacity to provide personalised feedback and suggestions for new lifestyle adoption (such as physical activity or promoting healthy eating habits)¹⁴ tailored to each participant's individual needs and preferences, which likely contributed to the success of the intervention. ¹⁵ This can help individuals to better manage their mental health, improve their overall well-being and thus diminish their risk of cancer.

There is strong justification for developing an eHealth platform that monitors users' behaviours and delivers adaptive, automated recommendations to promote behavioural change. Additionally, the platform can offer targeted professional support, reserved as a higher intervention level for participants facing greater challenges in adopting healthier lifestyle habits. This structure pursues efficiency, leveraging to all users automatic personalised guidance and health advice, and allowing professionals to focus on cases that have not adhered or responded to this first level of care.

Moreover, digital platforms enable continuous monitoring of individuals' behaviour and health status. However, the key challenge lies in minimising intrusiveness to ensure ecological assessment, thus promoting user adoption. In this context, automatic voice analysis has been explored as a promising digital biomarker to detect emotional distress and depression. Anxiety and stress are often reflected in vocal tension and irregular prosody, characterised by a faster speech rate, higher pitch, greater pitch variability, and an increased presence of pauses and hesitation markers, ¹⁶ along with elevated fundamental frequency. ^{17,18} Depressive symptoms are typically associated with reduced speech expressivity, such as slower speech rate, lower pitch and increased pauses and hesitation. ¹⁹

Altogether, the objective of this pilot study is to test the feasibility of delivering an accessible, usable, effective and efficient tool to the European population.

Additionally, wearable devices allow for the passive collection of a broad range of health indicators, including behavioural and psychosocial risk factors associated with cancer development. These technological tools provide a comprehensive, dynamic, and timely view of an individual's physical and psychological state by measuring physiological data and seamlessly gathering information without disrupting daily routines.²⁰ Beyond enhancing data collection, wearable devices play a crucial role in promoting patient engagement and compliance, as many users find them empowering and effective in boosting self-awareness.²¹ More importantly, they can support behavioural change and emotional management, which are key elements in the complex, multidisciplinary field of primary cancer prevention. Indeed, the continuous, timely data generated by these devices will not only strengthen the validity and reliability of our findings but, when integrated with traditional methods, can enable more accurate and less intrusive data gathering, monitoring, and potentially, in the future, the delivery of personalised interventions through the iBeChange platform.

Considering these advancements, a wearable sub-study has been included as part of this pilot study, involving a subsample of participants. The goal is to develop a passive and non-intrusive monitoring system that leverages wearable sensors to gather information about participants' health status, emotions, and lifestyle. This approach aims to enhance adherence and acceptance by potentially minimising the participants' burden in the future. Furthermore, the sub-study will assess the feasibility of integrating wearable devices to complement data already collected through questionnaires, allowing for more accurate detection and potential modification of risk factors. Ultimately, the sub-study will explore whether participants using wearables exhibit a higher degree of behavioural change and psychosocial adjustment compared to those not using these devices.

For this sub-study, smart rings will be used. Indeed, in recent years, the smart ring market has experienced significant growth due to increasing demand for discreet and non-invasive wearable devices. Smart rings represent an innovative category of wearables, standing out for their accuracy in biometric measurements, subtle design, and ease of use in daily life.^{22,23} Compared to smartwatches, smart rings offer a crucial advantage for clinical studies: their compact size and minimal visibility enhance compatibility with participants' existing wearable devices while reducing the risk of study dropout by lowering the perceived intrusiveness.

Specifically, the Oura Ring²⁴ has been selected for this sub-study due to its unique combination of continuous health monitoring capabilities and user-friendly design. It offers cross-platform compatibility, connecting seamlessly with both iOS and Android devices, and includes an API that allows remote data access via an external app, as the one developed within the iBeChange project. The ring's availability in multiple sizes ensures a comfortable fit for a wide range of anatomical differences, accommodating most of the population. Additionally, its long battery life, lasting up to 8 days, supports uninterrupted data collection, minimising user inconvenience. Furthermore, the Oura Ring ensures robust data security and privacy by storing collected data on servers located in countries compliant with General Data Protection Regulations (GDPR). By choosing the Oura Ring, this sub-study aims to strike a balance between data accuracy and participant comfort, ultimately fostering higher adherence rates and maximising the reliability of the collected data.

3.2. Risk/Benefit Assessment

3.2.1. Known potential risks

Regarding known potential risks, this is a pilot study of minimum risk since administered questionnaires (behavioural and psychosocial factors) and the digital intervention do not have risk of complications. It must be considered that participants might feel triggered by some questions (for example, those related to emotional well-being). Also, the number of questions to be answered may overwhelm participants.

The wearable sub-study presents potential risks that must be carefully considered. In fact, participants may experience discomfort or irritation from wearing the device, although the availability of multiple sizes should minimise this risk. Moreover, some participants might feel increased anxiety or stress when confronted with health data, which could affect their emotional well-being. Finally, technical issues, such as connectivity problems or battery failures, may occasionally disrupt data collection.

3.2.2. Known potential benefits

Regarding known potential benefits, the participants will benefit from closer behavioural and psychosocial monitoring, along with professional support if needed, during the study.

Among the benefits of the wearable sub-study, the use of wearables like the Oura Ring allows for continuous and passive health monitoring, ^{25,26} providing real-time insights into participants' physiological and behavioural patterns. Additionally, the non-intrusive design of the Oura ring is expected to improve user compliance, contributing to more reliable data collection.

This will allow for the accuracy of health assessments, support the identification of risk factors, and potentially foster proactive behavioural changes by increasing participants' awareness of their risky health habits and health metrics.

4. Study Design

4.1. Study objectives and design

The main aim of this pilot study is to assess the **feasibility** and to obtain preliminary data on the **effectiveness of the iBeChange intervention** in achieving targeted behavioural change for primary cancer prevention. Preliminary data on the **cost-effectiveness** of the intervention in comparison to the standard practice recommendations will also be evaluated.

Participants will be randomly assigned to two different groups: the experimental group (EG), receiving a digital stepped-care intervention (i.e., iBeChange; iBC) and the control group (CG), receiving the usual practice recommendations (UPR). The experimental intervention will last 12 weeks. Outcomes will be obtained at baseline, and at the end of the intervention.

The overall study design is a Bayesian adaptive trial. It will use Bayesian methods to update intervention effect probabilities as data accumulate, allowing for trial modifications based on interim analyses.

The iBeChange intervention targets habits on five key health areas associated with behavioural and psychosocial factors that have been shown to increase or reduce cancer risk. These areas, referred to as **Health Pillars**, include:

- Smoking
- Alcohol consumption
- · Nutrition and body weight
- Physical activity
- Emotional well-being (including stress, anxiety, depression, social support, and sleep)

As a result, the effectiveness outcomes of the study focus on changes in these health behaviours and psychological symptoms. Further details can be found in the following table and in Section 4.4: Effectiveness Data Collection.

4.2. Study endpoints

Table 3 summarises the primary, secondary and tertiary objectives and endpoints of this pilot study:

Table 3. Objectives and endpoints in the iBeChange Pilot Study (next page)

Objectives	Endpoints	Justification for endpoints	Collected measures
Primary			

Objectives	Endpoints	Justification for endpoints	Collected measures
To assess the feasibility of the iBeChange intervention ²⁷	sibility of theCapability and Resulting Samplestudy is to assess whether the conduction of a clinical	 Recruitment number and rate per centre and in total Completion of study questionnaires at baseline and after 12 weeks for 	
		randomised controlled trial with a recruitment size ten	measuring the intervention's effectiveness
	Acceptability and Suitability of Intervention and	33.00	Potential difficulties in the recruitment process
	Study Procedures • Resources and		 System Usability Scale to assess the usability of the platform and participants
	Ability to Manage and Implement		feedback collection • Feedback from study
	the Study and Intervention		personnel on workload and areas for improvement
Secondary		 	improvement
•	- Proliminary	We hypothesise that the	Pahavioural change
To preliminary assess the effectiveness and cost-effectiveness of the intervention	 Preliminary Responses to Intervention 	We hypothesise that the iBeChange intervention will be effective in achieving BC towards habits more compliant with cancer prevention guidelines. To preliminary assess its effectiveness, measures on	 Behavioural change outcomes: Smoking: Seven-day point prevalence abstinence; Change in Smoking habits Fagerström test for Nicotine Dependence (FTND)
		behavioural change habits and emotional well-being symptoms will be obtained before and after the	Alcohol: Alcohol Use Disorders Identification Test (AUDIT)
		intervention in the control and experimental groups. We also hypothesise that	Nutrition: iBeChange-Die questionnaire on Cancer Nutritional factors; Heigh
		this solution will be cost- effective compared to	and Weight for BMI calculation
		standard healthcare. With the data collected, the	Physical activity: Global Physical Activity Questionnaire (GPAQ)
		iBeChange platform can be improved and tested in a randomised controlled trial	Emotional well-being outcomes:
		with a recruitment size ten times bigger.	

IBeCHANGE

ID: 101136840

IBe	CH.	ΑN	GE
ΙD·	101	136	5840

Objectives	Endpoints	Justification for endpoints	Collected measures
			Perceived Stress: Perceived Stress Scale (PSS-4)
			Anxiety and Depressive symptoms: Patient Health Questionnaire (PHQ-4)
			Perceived Social Support: Perceived Social Support (F-SozU K-3)
			Cost-effectiveness:
			Cost-effectiveness PECUNIA Resource Use Measurement (PECUNIA RUM) Instrument
			EQ-5D-5L Quality of Life
Tertiary/Explora	tory		
Voice analysis			
To assess the feasibility of using voice biomarkers to derive information about emotional distress	Preliminary concurrent validity (accuracy of machine learning algorithm on voice signals to automatically classify emotional distress)	Achieving a high accuracy of machine learning algorithms is essential to confirm that voice signals can be used as valid biomarkers of emotional distress.	Voice recordings (raw data) Emotional distress thermometer
Wearable Sub-stud	у		1
To test the feasibility and suitability of wearables to complement psychosocial and behavioural features in a health intervention. To assess the correlation between wearable data	• Feasibility assessed through the completion rate of wearable data collection and the percentage of successful data transmissions without technical issues. The times a ring size is not available at site for a participant	Assessing data completion rates and successful transmissions demonstrates whether wearables can reliably collect and transfer data to support the intervention. Data from wearables logistics will allow to adjust ring size purchases and distribution among clinical sites. Investigating participant	Physical activity: number of steps; metabolic equivalent of task (MET) (1-minute intervals); average MET minutes (average MET level sustained throughout the day, factoring in all activities and rest periods); high activity MET minutes and High activity time; low activity MET minutes and low activity time; medium

Objectives	Endpoints	Justification for endpoints	Collected measures
and self-reported measures. To assess whether wearable data can improve the effectiveness of personalised recommendation s delivered by the recommender system in the intervention in future settings. To compare user's adherence and usability of the system between participants in the wearable substudy and those in the standard iBeChange group.	will also be registered Suitability evaluated via participant-reported satisfaction and perceived ease of use of wearables, measured through post-intervention questionnaires. Preliminary concurrent validity (correlation between wearable data with self-reported outcome measures in domains such as physical activity and psychosocial health). Changes in primary and secondary outcomes between participants in the wearable sub-study and the standard iBeChange group to evaluate the preliminary impact of the use of wearables on the intervention. Changes in satisfaction and adherence rates between participants in the wearable on the intervention.	ease of use helps determine if wearables are suitable for complementing the monitoring of psychosocial and behavioural health. Validating the correlation between wearable data and self-reported measures is essential to confirm that wearables can assess psychosocial and behavioural constructs. Comparing changes between groups helps evaluate whether wearables, by providing objective and timely data, can enhance the personalisation and effectiveness of the iBeChange intervention. Analysing usability and adherence reveals whether the use of wearables increases participant engagement, positively impacting their involvement in the intervention.	medium activity time; sedentary MET minutes and sedentary time; inactivity alerts; active calories (calories burned during physical activity); total calories (total number of calories burned during the day) • Psychosocial health: • Sleep data: heart rate; heart rate variability; latency (time it takes to fall asleep from the moment the subject gets into bed); temperature deviation; restless period; average breath; efficiency (ratio of time actually spent sleeping to the total time spent in bed); sleep score; light, deep and REM sleep time; readiness score (body's recovery status and physical preparedness); startend bed time. • Stress Resilience: daytime stress (in terms of heart rate, heart rate variability, motion and temperature throughout the day). • Satisfaction and usability of smart ring use

Objectives	Endpoints	Justification for endpoints	Collected measures
	sub-study and those in the		
	standard		
	iBeChange group.		

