6.2.1. Intervention levels

The stepped care intervention will contain the following intervention levels:

- Level 0: In this intervention level, **automatic** recommendations and resources will be delivered to support the achievement of the weekly missions. Among these, the possibility to enter a group chat for social support among participants named iBeChange community can also be assigned.

Once every 4 weeks, the full health habit assessment (for more detail, refer to section 6.2. on the page before) will be administered (at baseline, 4 weeks, and 8 weeks).

In addition to the weekly mission monitoring, the emotional distress thermometer in the visual analogue scale (0-10) form will be assessed every 2 weeks. In case the answer > 5, PSS-4 and PHQ-4 will be administered to detect stress, anxiety or depression levels. If any of these are moderate or high, participants will be escalated to Level 1.

If the participant agrees to voice recording, after the emotional distress thermometer assessment, the question "How stressed do you feel right now?" will be displayed asking users to speak and record the answer.

- Level 1: In this intervention level, participants will be able to contact a **healthcare professional** via chat to solve doubts about their behavioural change strategy or emotional well-being status. This interaction will be initiated by the participant.
- Level 2: Participants in this level will receive a single-session healthcare professional intervention. This will be a one-hour online session with a motivational interview structure, in which the participant's needs and potential barriers for behavioural change will be addressed.

Techniques and interventions with effective evidence will be administered according to the participant's symptom or situation.

To standardise intervention Level 2, a detailed professional single-session protocol has been developed. After the session, professionals will register the techniques used for proper monitoring of the intervention.

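### The exploratory voice endpoint rests on accuracy alone, which can look high with no ability to detect distress if distress is uncommon in this sample

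*Protocol*

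**What the plan says.** Table 3 (Protocol Section 4.2) lists voice analysis under the tertiary/exploratory objectives. The objective is a feasibility one: "To assess the feasibility of using voice biomarkers to derive information about emotional distress". The endpoint is "Preliminary concurrent validity (accuracy of machine learning algorithm on voice signals to automatically classify emotional distress", and the justification reads "Achieving a high accuracy of machine learning algorithms is essential to confirm that voice signals can be used as valid biomarkers". No other performance measure is named, and no value is attached to a high accuracy.

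The data come from the procedure in Section 6.2.1. There, "the emotional distress thermometer in the visual analogue scale (0-10) form will be assessed every 2 weeks". Participants who agreed to voice recording are then shown a prompt, "How stressed do you feel right now", and answer it aloud. The only thermometer cut-off in the protocol stands in the same section: "In case the answer > 5, PSS-4 and PHQ-4 will be administered to detect stress, anxiety or depression levels". It triggers further questionnaires and is not given as the class boundary for the voice classifier.

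On the sample, the Synopsis (Section 2.1) says "This pilot study will enrol a total of 180 healthy individuals (60 per clinical centre", and these people attend cancer screening. Section 5.2 limits recording to consenting members of the experimental group, which Section 8.2 sets at 90 people.

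**The concern.** Accuracy mixes sensitivity and specificity in proportions set by the prevalence of the condition. When one class dominates, accuracy mostly reports the size of that class. People attending screening and described as healthy may well give few recordings labelled as distressed. In that case a high figure would say little about whether the voice carries information on distress, and a useless classifier could score above a useful one. Since Table 3 ties the conclusion on validity to this one measure, the pilot could report an encouraging voice result that its data do not support.

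**Working it through.** The protocol states no accuracy target, distress prevalence or sample size for the voice analysis, so there is no figure to reproduce. The check is of how the named measure behaves.

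**1. Accuracy and prevalence.** Let p be the share of recordings labelled distressed (an assumption throughout).

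Accuracy = sensitivity × p + specificity × (1 − p).

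- Never-detect classifier: sensitivity 0, specificity 1, so accuracy = 1 − p.
- Moderately useful classifier: sensitivity and specificity both 0.75, so accuracy = 0.75p + 0.75(1 − p) = 0.75 at every p.

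| Assumed p | Accuracy, never-detect | Accuracy, 0.75/0.75 classifier |
|---|---|---|
| 5% | 0.95 | 0.75 |
| 10% | 0.90 | 0.75 |
| 20% | 0.80 | 0.75 |
| 25% | 0.75 | 0.75 |
| 30% | 0.70 | 0.75 |
| 40% | 0.60 | 0.75 |
| 50% | 0.50 | 0.75 |

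The ranking reverses where 1 − p > 0.75, that is, for p below 25%. The mean of sensitivity and specificity gives the never-detect classifier (0 + 1)/2 = 0.50 at every p. Its AUC is also 0.50, because it ranks nobody.

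**2. Precision of sensitivity.** At most 90 people can record. With one label per person and full consent, p = 10%, 20% and 30% give 90 × p = 9, 18 and 27 distressed people. Wilson 95% intervals around a sensitivity of about 0.75 are then roughly 0.43-0.92, 0.52-0.89 and 0.56-0.87. Lower consent widens them. Intervals therefore need to accompany the estimates.

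**3. Repeated recordings.** One recording every 2 weeks for 12 weeks is 12/2 = 6 per person, so at most 90 × 6 = 540 recordings from 90 speakers. If recordings of one speaker fell in both training and test data, a model could score by recognising the speaker. A simulation shows the possible size. It used 45-60 speakers with 6 recordings each, 20 features carrying speaker identity but nothing on distress, within-person correlation of distress 0.4 or 0.6, p from 10% to 30%, a 4-nearest-neighbour classifier and 5-fold cross-validation. Splitting by recording gave an AUC of 0.68-0.80. Holding out whole participants gave 0.48-0.51, which is chance. These settings are assumptions, and the protocol does not say how the data will be split.

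**4. Spoken content.** The rationale (Section 3.1) relies on vocal markers such as pitch, speech rate and pauses. The prompt in Section 6.2.1 comes directly after the 0-10 rating and asks about stress, so the words of the answer can repeat the rating that serves as the reference.

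**The case against.** The strongest reply is that Table 3 is a summary, that the endpoint is called preliminary and is exploratory, and that accuracy may be shorthand for classification performance. Metrics, cut-off and validation scheme may stand in an analysis plan that is not shown, so their absence from the protocol is no fault. That is right about the missing detail. It does not remove the point, because accuracy is the measure the protocol does name.

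Several stronger readings are tempting and are not supported:

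- *That the biomarker will be declared valid on accuracy alone.* The text makes high accuracy a necessary condition and does not say that it suffices.
- *That a never-detect classifier would meet the criterion.* With no number attached, one can say only that it could.
- *That the sample is mostly undistressed.* No prevalence is given. Being called healthy is indirect evidence; Section 5.1 does not exclude severe mental illness automatically, and emotional well-being is one of the targeted pillars (Section 4.1).
- *That a score above 5 defines distress for the classifier.* It is only the questionnaire trigger, and another boundary would change p.
- *That the plan commits speaker leakage or feeds spoken words to the model.* It describes no data split and no transcription. Sections 3.1 and 5.2 point to vocal markers.
- *That an inflated result would carry a voice model into the RCT.* Section 8.8 does not mention voice, and where the Conclusions (Section 11) speak of validating tools, the examples are REDCap and the Point of Care platform.

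**Conclusion.** The point holds in limited form. Accuracy is a poor sole measure for this endpoint if distress is uncommon among the recordings. At an assumed prevalence of 10-30%, 90-70% accuracy is available with no detection at all, and below 25% accuracy ranks that empty classifier above one with sensitivity and specificity of 0.75. The conclusion depends on low prevalence, which is plausible but not documented. Speaker recognition and spoken content are reasons for safeguards in the remedy, not errors in the protocol. Severity is minor: no primary or secondary endpoint, interim rule or stated trial decision uses the voice result.

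**What to change.** In Table 3, replace accuracy in both the endpoint and its justification by AUC, with sensitivity and specificity at a thermometer cut-off fixed before analysis. Report the majority-class accuracy beside them as the reference.

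Add two safeguards, there or in the analysis plan:

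- Estimate performance with all recordings of a participant held out together, and give participant-clustered intervals.
- State that the model uses the acoustic and prosodic features named in the rationale, so that the words of the answer do not enter it.

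The cost is a change of wording and slightly more analysis, with no new data collection. The downside is that reported performance will look less favourable and, with few distressed participants, visibly imprecise.
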